Pregnancy: For approved indications, the fluconazole dosage used in this protocol is classified as category D risk for pregnant females. Category D risk indicates there is positive evidence of human fetal risk, including increased risk or rates of miscarriages, based on adverse reaction data from investigational or marketing experience or studies in humans. However, potential benefits may warrant use of the drug in pregnant women despite potential risks. A few published case reports describe a rare pattern of distinct congenital anomalies in human infants exposed in utero to doses between 400-800 mg/day of fluconazole. The risk benefit ratio for fluconazole when used in this protocol is still unknown, thus pregnant women will be excluded from participating in this study. In addition, pregnancy testing will be performed in all women of childbearing potential prior to randomization and throughout the duration of the study intervention. All women of childbearing potential will be required to use a highly effective method of birth

control. Any pregnancy will be cause for discontinuation of active treatment and will be followed for up to two months after birth to assess for potential adverse effects to the fetus.

Other unknown risks, discomforts, or side effects: There is a theoretical risk that early treatment may modify the host response and that treatment will impair host control and may lead to more relapses after treatment is eventually stopped.

Electrocardiogram (ECG): Mild skin irritation from the application and/or removal of the ECG patches is possible.

Blood sampling: Drawing blood may cause transient discomfort and fainting. Fainting is usually transient and managed by having the subject lie down. Bruising at the blood draw site may occur, but can be prevented or lessened by applying pressure to the draw site for several minutes.

Drawing blood may also cause infection. The use of aseptic technique will make infection at the site where blood will be drawn extremely unlikely.

Nasopharyngeal swab: Side effects of collecting a nasal pharyngeal swab may include mild discomfort and/or irritation of the nasal passage, occasional gagging, and rarely bleeding of the nasal passage.

Throat swab: Side effects of collecting a throat swab may include mild discomfort and/or irritation of the throat passage and occasional gagging.

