This primary analysis will be performed in the cocci-positive per-protocol population of subjects who meet the case definition of coccidioidomycosis pneumonia and who were adherent to the intervention administration (See Section 11.4.1). As defined below, adherence will be defined as taking at least 80% of the study medication (fluconazole or placebo) as determined at the day 22 visit. Pill count, if available, will take precedence over patient report of adherence.

Case Definition

The case definition of coccidioidomycosis pneumonia is met if the is subject diagnosed with CAP at the time of enrollment as determined by the referring health care provider, and meets one of the following serologic criteria:

1. The patient is positive for any two serologic tests at any time point from Day 1 through Day 29. The two positive results can but do not necessarily have to be from the same assay or the same time point. The assays considered for this criteria are: Immunodiffusion testing [IDTP (IgM) and IDCF (IgG)]; Enzyme linked immunoassay testing (EIA-IgM and EIA-IgG); OR
2. The patient is negative for anti-*Coccidioides* antibody by immunodiffusion assay (or EIA-IgG) at Day 1 and sero convert to positive for anti-*Coccidioides* antibody by immunodiffusion assay (or EIA-IgG) at any time point after Day 1 through Day 29; OR
3. The patient is negative or indeterminate for anti-*Coccidioides* antibody by CF assay on Day 1 and demonstrates a titer of greater than or equal to 2 by CF assay at any point after Day 1 through Day 29; OR
4. The patient is positive for anti-*Coccidioides* antibody by CF assay on Day 1 and demonstrates a rise of greater than or equal to 2-fold dilution in Complement Fixation (CF) titer compared to baseline at any time point after Day 1 through Day 29.

All serologic testing for a single participant from Day 1 through Day 29 will be batched and run concurrently to eliminate confounding due to test run variability.

Adherence

Adherence in all subjects will be assessed by patient self-report and pill count according to standard procedures, on Days 22, 29 and 43. Pill count, if available, will take precedence over patient report. If pill count is not available, patient report will be used.

To be considered adherent at a visit when the clinical response is measured, the subjects will need to have taken at least 80% of their expected pills.

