- Dyspnea (Shortness of breath)
- Sputum production
- Night Sweats
- Fever
- Hypoxia

Exploratory Outcome 5:

- Repeat the analysis of the Primary Objective, and secondary objectives 1-6 with the alternative serologic case definition (see [Table 4](#)).

Table 4: Case Definition 2 (Alternative Case Definition for Exploratory Analyses)

Patients who meet at least one of the following criteria are considered cases [#] :
Patient is negative for anti- Coccidioides antibody by complement fixation (CF) assay on Day 1, and demonstrates a titer of greater than or equal to 2 by CF assay at both Days 22 and Day 29
Patient is negative for anti- Coccidioides antibody by complement fixation (CF) assay on Day 1, and demonstrates a titer of greater than or equal to 4 by CF assay at either Day 22 or Day 29
Patient is negative for anti- Coccidioides antibody by immunodiffusion CF (IDCF, IgG) on Day 1, and has a positive IDCF test on either Day 22 or Day 29
Patient is negative for anti- Coccidioides antibody by immunodiffusion TP (IDTP, IgM) on Day 1, and has a positive IDTP test on either Day 22 or Day 29
Patient is negative for anti- Coccidioides antibody by enzyme linked immunoassay testing (EIA-IgM) on Day 1, and has positive EIA-IgM at both Days 22 and Day 29
Patient is negative for anti- Coccidioides antibody by enzyme linked immunoassay testing (EIA-IgG) on Day 1, and has positive EIA-IgG at both Days 22 and Day 29
All serologic testing for a single participant from Day 1 through Day 29 will be batched and run concurrently to eliminate confounding due to test run variability.
Absolute values will be recorded for serologic tests, where appropriate, and Indeterminate/Equivocal test results will be treated as a Negative test.

Exploratory Outcome 6:

- The mean, median, and quartiles of the FLEET CAP score at Day 1 in subjects who meet the protocol defined primary case definition and subjects who do not meet the protocol defined primary case definition.

-
- The mean, median, and quartiles for each component of the FLEET CAP score at Day 1 in subjects who meet the protocol defined primary case definitions and subjects who do not meet the protocol defined primary case definition.
 - Cough
 - Fatigue
 - Chest Pain
 - Dyspnea (Shortness of breath)
 - Sputum production
 - Night Sweats
 - Fever
 - Hypoxia

Exploratory Outcome 7:

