11.2. Sample Size Considerations

11.2.1. Sample Size for Per Protocol Analysis Population

The primary analysis will compare the proportion of subjects achieving clinical response at Day 22 among efficacy evaluable subjects, defined as subjects in the Cocci-Positive Per Protocol analysis population who meet the case definition of coccidioidomycosis pneumonia who were compliant with the intervention administration and have coccidioidal serology data available at the Day 1 and 22 visits. We further assume that the clinical response proportion at Day 22 will be 0.20 in the placebo arm, and 0.40 in the fluconazole arm. As described in section 11.2.3, enrollment will continue until 200 subjects are evaluable for efficacy, 100 in each treatment arm, which suffices for 88% power for the Z test with unpooled variance to compare proportion of clinical responses at Day 22 at the two-sided level of 0.05. This is the primary sample size calculation which forms the basis for target enrollment to the study and for subsequent sample size re-estimation procedures at scheduled interim analyses while the study is enrolling.

A secondary analysis in the Cocci Positive Modified Intent-to-Treat population will compare the proportion of responders at Day 22, treating subjects dropping out before the Day 22 visit as non-responders. Assuming that the probability of drop-out before Day 22 is 20% among cocci-positive subjects, we would expect that 250 cocci-positive subjects would be available for this secondary analysis as a result of reaching the target sample size of 200 cocci-positive subjects with Day 22 follow-up for the primary analysis. Since subjects who drop-out are considered non-responders, the probability of response in the control-arm subjects would be $0.8 * 0.2 = 0.16$, and in the treated subjects would be $0.8 * 0.4 = 0.32$. The Z-test with unpooled variance has power of 85% to detect this difference in response proportions with 125 cocci-positive subjects per arm.

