11.4.4.1. Primary Efficacy Analysis

The primary efficacy analysis tests the difference between the fluconazole and placebo treatment groups in the proportion of subjects with an occurrence of clinical response at Day 22. Subjects without a clinical response at Day 22 will be coded as treatment failures while subjects with a clinical response at Day 22 will be coded as an observed event if the clinical response outcome measure definition (Section 3.2.1) is met.

A test of difference between the proportion of clinical responses in the fluconazole and placebo groups at the Day 22 time point will be performed using the Z test. The use of this test statistic will permit us to use the method of B-values to calculate conditional power of the test in the planned futility analyses, as outlined in “Statistical Monitoring of Clinical Trials, a Unified Approach”, by Proschan et al [22]. Details of this procedure will be provided in the statistical analysis plan.

The primary efficacy analysis will be performed in the cocci-positive per protocol analysis population. Secondary analyses will be performed in the all randomized per protocol population, all randomized and cocci-positive ITT and the mITT populations (see also Secondary Objectives 1 and 6). Sensitivity analyses, which will assess the impact of drop-out, censoring mechanisms, and analysis methods on the primary analysis, may be performed. These analyses will be specified in the separate statistical analysis plan document.

In addition to the planned tests of hypotheses, descriptive analyses will be performed for the primary endpoint. The number of clinical responses observed will be tabulated by time point, including and beyond Day 22, and treatment group. Tabular and graphical summaries will be prepared for the composite MSG score across all assessment time points.

To investigate whether there is evidence of a differential diagnosis of coccidioidomycosis between treatment arms, which might result in selection bias for inclusion in our primary analysis, the number of coccidioidomycosis cases in each treatment arm will be compared among all randomized subjects.

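### Membership of the primary population depends partly on serology drawn on treatment, and the one check named for the resulting bias is insensitive and has no stated method or consequence

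*Combined protocol and SAP*

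**What the plan says.** Section 3.2.1 gives four serologic routes to case status. The first is "The patient is positive for any two serologic tests at any time point from Day 1 through Day 29"; the two results may come from different assays at one visit, so Day 1 serum alone can suffice. Routes 2 to 4 each need a result after Day 1. Study drug starts at the Day 1 visit (7.2), so Day 22 and Day 29 sera are drawn on treatment. The cocci-positive per-protocol population (11.4.1) also requires adherence and available Day 1 and Day 22 serology.

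Section 2.3.1 states: "There is a theoretical risk that early treatment may modify the host response". Section 3.1.3 makes the effect of fluconazole on the immune response to the infection an exploratory objective.

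Section 11.4.4.1 says that a differential diagnosis between arms is to be investigated, because of a mechanism "which might result in selection bias for inclusion in our primary analysis". The investigation is a comparison of the number of cases by arm among all randomized subjects. No test, level, interval, threshold or follow-up action is given. The sensitivity analyses in that section are optional and cover drop-out, censoring and analysis methods, not selection by serology.

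**The concern.** Randomization makes the arms comparable as randomized. It does not protect a subset whose membership is decided partly by a laboratory result that treatment might change. If fluconazole reduced or delayed antibody detection, some fluconazole-arm subjects would fail the case definition although they would have met it on placebo. If those subjects respond differently from the other cases, the primary contrast mixes the effect on response with an effect on who is counted.

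The plan sees this. The question is whether its named safeguard could reveal a problem of a size that matters, and whether another planned cocci-positive analysis is free of it. The cocci-positive mITT population uses the same case definition. The alternative definition in Table 4 is more exposed: every route needs a negative Day 1 result and a positive one on Day 22 or Day 29, for example a subject who "demonstrates a titer of greater than or equal to 2 by CF assay at both Days 22 and Day 29".

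**Working it through.** **Inputs from the documents (11.2.1, 11.2.3, 5.3.1).** Response rates: "We further assume that the clinical response proportion at Day 22 will be 0.20 in the placebo arm, and 0.40 in the fluconazole arm". Evaluable subjects: "enrollment will continue until 200 subjects are evaluable for efficacy, 100 in each treatment arm". Test: "which suffices for 88% power for the Z test with unpooled variance", "at the two-sided level of 0.05". Enrollment is 1,000 at 1:1, so 500 per arm. The case rate is 20%, or 25% if the 250 cocci-positive subjects expected for the mITT analysis are used (250/1,000).

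**Assumptions.** f is the share of would-be fluconazole-arm cases that treatment removes; the documents give no value. The count comparison is taken as a two-sided 0.05 Z test, since no level is stated.

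**1. The plan's own figure.** SE = √(0.2·0.8/100 + 0.4·0.6/100) = 0.0632; 0.20/0.0632 = 3.16; power = Φ(3.16 − 1.96) = 88.5%. With pooled variance it is 87.6%, as in Table 5. The stated 88% reproduces.

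**2. Power of the count comparison, 500 per arm.** Compare p with p(1 − f), with SE = √[p(1−p)/500 + p(1−f)(1−p(1−f))/500]. For p = 0.20 and f = 10%: 0.02/0.0248 = 0.81, power 12.7%.

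| Loss f | Case rate 20% | Case rate 25% |
|---|---|---|
| 10% | 13% | 15% |
| 20% | 38% | 47% |
| 25% | 55% | 67% |
| 30% | 72% | 83% |

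Power of 80% needs f of about 33% (20.0% vs 13.4%) or 29% (25.0% vs 17.7%).

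**3. What equal counts leave open.** The 95% interval for the difference in case rate has half-width of about 1.96·√(2·0.2·0.8/500) = 5.0 points at a 20% case rate, and 1.96·√(2·0.25·0.75/500) = 5.4 points at 25%. Identical counts would thus be compatible with a relative loss of roughly 5.0/20 = 25% or 5.4/25 = 21%.

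**4. Effect on the primary estimate.** Take 100 placebo cases with 20 responders, and 100 would-be fluconazole cases with 40 responders.

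| Loss | Lost cases | Observed fluconazole rate | Difference |
|---|---|---|---|
| 10% | all responders | 30/90 = 0.333 | 13.3 points |
| 10% | 80% respond | 32/90 = 0.356 | 15.6 points |
| 10% | 40% respond, like the rest | 36/90 = 0.400 | 20.0 points, no bias |
| 10% | all non-responders | 40/90 = 0.444 | 24.4 points |
| 20% | all responders | 20/80 = 0.250 | 5.0 points |
| 20% | all non-responders | 40/80 = 0.500 | 30.0 points |

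For the 10% loss, primary power falls from 88% to 55% in the first row and to 68% in the second.

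Under the null (0.20 in both arms) with a 20% loss, the rejection rate is 12.5% if all lost cases are non-responders (20/80 = 0.25 vs 0.20). It is about 7% if they respond at 10% (18/80 = 0.225 vs 0.20).

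**5. The all-randomized analyses.** With the plan's 0.64 and 0.672 (11.2.1) and 500 per arm: 0.032/0.0300 = 1.07, giving about 19% power for superiority.

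**The case against.** A reader might infer that the whole primary population is selected on treatment. It is not: criterion 1 can be met on Day 1 serum alone, and the share of such cases is not given.

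A reader might also infer that nothing else in the plan bears on the problem. Exploratory outcome 1 compares time to first positive antibody by arm through Day 43, which looks at the mechanism directly. The ITT and all-randomized mITT and per-protocol analyses are not selected on case status. This stands, but it does not close the gap. The antibody outcome omits EIA, which the case definition uses, and does not quantify bias in the primary estimate. The all-randomized analyses are heavily diluted. The separate SAP announced in 11.4.4 is not in the text reviewed and may contain more.

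The evidence that treatment alters serology is thin. The sentence in 2.3.1 goes on to impaired host control and relapse, not seroconversion. Table 4 is offered in 11.2.2 for misclassification, not as a check on this bias. The plan nowhere says that a non-significant count comparison would be read as reassurance; the supported criticism is that it does not say how the result would be read. Finally, the outer figures above are extremes, and a loss of about a third or more would probably be detected.

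**Conclusion.** The point holds in limited form. Membership of the primary population depends partly on on-treatment serology, the plan acknowledges the risk, and the one check named for it would usually miss a loss of 10-20% of fluconazole-arm cases (power 13-15% and 38-47%). Losses of that size can matter if the lost cases respond differently, and equal counts do not show that the remaining cases are alike.

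The documents do not support the stronger conclusion that the primary estimate is biased or that its type I error is inflated. Both need a loss rate and a response pattern that the documents do not give. The calculations rest on assumed losses, an assumed two-sided 0.05 level for the count comparison, 500 per arm, and a case rate of 20-25%. This is a change the plan should make; it is not a reason to abandon the primary analysis.

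**What to change.** Keep the primary definition and analysis. Add to 11.4.4.1, or to the separate SAP:

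- **Day 1 serology subset.** A pre-specified sensitivity analysis of Day 22 response by randomized arm in all treated subjects who meet criterion 1 on Day 1 serum alone, regardless of adherence or availability of Day 22 serology. Count drop-outs before Day 22 as non-responders, as 11.2.1 does for the cocci-positive mITT analysis. Keeping the per-protocol conditions would bring post-randomization selection back in.
- **Case-rate difference.** A 95% confidence interval for the arm difference in case rate among all randomized subjects, with a statement that a non-significant difference is not evidence of no selection.
- **Optional tipping-point analysis.** Over a pre-stated range of case loss (for example 0 to 33%, the upper end being where the count comparison reaches 80% power at a 20% case rate), report the response rate among lost cases at which the primary conclusion changes.

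Do not instead bound the estimate by adding the observed difference in case numbers back to the smaller arm. With 500 per arm, a 20% case rate and no selection, chance alone gives a difference of 10 or more cases in 45% of trials. A true 10% loss shows no deficit on fluconazole in 22%.

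The cost is wording and analyses on sera already scheduled for collection and assay. The Day 1 subset is smaller and less precise, by an amount that cannot be stated in advance. It represents subjects already seropositive at presentation, so agreement with the primary result supports that result without proving the later-diagnosed cases free of selection.

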11.4.4.2. Secondary Efficacy Analyses

Table 11 below briefly outlines the analytic approaches that will be taken for the secondary efficacy analyses. Details of the analyses will be described in the separate statistical analysis plan document.

Table 11: Secondary Efficacy Analyses

Secondary Objective	Outcome Measure	Main Analytic Strategy
(SO 1): To assess the clinical response of early empiric antifungal therapy with fluconazole at Day 22 in subjects with coccidioidomycosis pneumonia regardless of adherence with the study intervention.	Proportion of clinical response at Day 22 regardless of adherence to the study intervention in each treatment group.	Repeat the primary efficacy analyses in the all randomized mITT, cocci-positive mITT, and ITT populations.
(SO 2): To assess the clinical response of early empiric antifungal therapy with fluconazole at Day 43 in subjects with coccidioidomycosis pneumonia regardless to adherence with the study intervention.	Proportion of clinical response at Day 43 regardless of adherence to the study intervention in each treatment group.	Repeat the analyses for SO 1 using Day 43 as the time point for the outcome measure instead of Day 22 as well as perform a time-to-event analysis. This analysis will be performed in the all-randomized mITT, cocci-positive mITT, and ITT populations.

(SO 3): To compare the clinical response and its individual components by study group, over time, in subjects with coccidioidomycosis pneumonia.
	
The mean, median, and quartiles of the FLEET CAP score at Days 22, 29 and 43 in each treatment group.
 
The mean, median, and quartiles for each component of the FLEET CAP score at Days 22, 29 and 43 in each treatment group.
 
 1. Cough 2. Fatigue 3. Chest Pain 4. Dyspnea (Shortness of breath) 5. Sputum production 6. Night Sweats 7. Fever 8. Hypoxia 	
Descriptive and/or graphical summaries of the outcome measures by treatment group. This analysis will be performed in both PP populations, both mITT populations, and the ITT population.


(SO 4): To assess the impact of early empiric antifungal therapy with fluconazole on days lost from work or school and responses to the SF-12v2 and PROMIS Item Bank v2.0 - Ability to Participate in Social Roles and Activities - Short Form 4a in subjects with coccidioidomycosis pneumonia.
	
Number of days of school or work missed after the start of the treatment through Day 43 in each treatment group.
 
The mean, median, and quartiles for the mental component summary (MCS) and physical component summary (PCS) scores of the SF-12v2 instrument and the responses to the individual items of the PROMIS Item Bank v2.0 - Ability to Participate in Social Roles and Activities - Short Form 4a at Days 22, 43, 90 and 180 in each treatment group.
	
Descriptive and/or graphical summaries of the outcome measures by treatment group. This analysis will be performed in both PP populations, both mITT populations, and the ITT population.

(SO 5): To assess the effect of early empiric antifungal therapy with fluconazole through Day 43 in subjects with coccidioidomycosis pneumonia on all-cause mortality by treatment group.
	
Incidence rate of all-cause mortality after the start of treatment and through Day 43 by treatment group.
	
Descriptive summaries of the outcome measure by treatment group. This will be performed in both PP populations, both mITT populations, and the ITT analysis population.

(SO 6): To assess whether early empiric antifungal therapy with fluconazole at Day 22 is non-inferior to placebo as defined by clinical response at Day 22 in all randomized subjects, regardless of coccidioidomycosis pneumonia status or adherence with study intervention, with baseline and follow-up FLEET-CAP scores.
	
Proportion of clinical response at Day 22 among all randomized subjects, regardless of coccidioidomycosis status or adherence with study drug, in each treatment group.
	
Two-sided level .05 test of non-inferiority based on whether the 95% confidence interval for the difference in estimates of 22-day response proportions excludes an absolute difference of .05 in favor of the placebo arm. This analysis will be performed in the ITT population.

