3.1.2. Secondary

- To assess the clinical response of early empiric antifungal therapy with fluconazole at Day 22 in subjects with coccidioidomycosis pneumonia regardless of adherence with the study intervention.
- To assess the clinical response of early empiric antifungal therapy with fluconazole at Day 43 in subjects with coccidioidomycosis pneumonia regardless of adherence with the study intervention.
- To compare the clinical response and its individual components over time, by treatment group, in subjects with coccidioidomycosis pneumonia.
- To assess the impact of early empiric antifungal therapy with fluconazole on days lost from work or school and responses to the SF-12v2 and PROMIS Item Bank v2.0 - Ability to Participate in Social Roles and Activities - Short Form 4a in subjects with coccidioidomycosis pneumonia.
- To assess the effect of early empiric antifungal therapy with fluconazole through Day 43 in subjects with coccidioidomycosis pneumonia on all-cause mortality by treatment group.
- To assess whether early empiric antifungal therapy with fluconazole at Day 22 is non-inferior to placebo as defined by clinical response at Day 22 in all randomized subjects, regardless of coccidioidomycosis pneumonia status or adherence with study intervention, with baseline and follow-up FLEET-CAP scores.

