11. STATISTICAL CONSIDERATIONS

11.1. Study Hypotheses

The primary objective of the study is to assess the clinical response of early empiric antifungal therapy with fluconazole at Day 22 in subjects with coccidioidomycosis pneumonia.

The study is designed to test the following hypothesis in the primary efficacy analysis conducted in the cocci-positive per protocol analysis population (see Section 11.4.1):

Null hypothesis: “The proportion of subjects with coccidioidomycosis pneumonia with protocol-defined clinical response is the same in the cohort of subjects receiving fluconazole as compared to placebo.”

Alternative hypothesis: “The proportion of subjects with coccidioidomycosis pneumonia with protocol-defined clinical response is different in the cohort of subjects receiving fluconazole as compared to placebo.”

The study design and primary hypothesis is based on the following parameters supplied by subject matter experts:

- The composite score will be sensitive to changes in the course of disease as a result of empiric treatment with fluconazole.
- A 50% reduction in composite score is a clinically meaningful reduction which has been used as a measure of clinical response in other trials.
- A Day 22 time point will be optimal for measuring clinical response as compared to a longer time point because subjects in both study arms will eventually resolve disease,
- The proportion of subjects responding at Day 22 will be 0.20 and 0.40 in the placebo and fluconazole arms, respectively.

However, there is considerable uncertainty in the design parameters, as they are based on natural history studies, and this is the first randomized trial of empiric therapy with fluconazole for coccidioidomycosis. The most important contribution of this trial may be to confirm or refute these assumptions and set the stage for future trials.

Several of the secondary and exploratory objectives in the trial are focused on validating the sensitivity of the composite score, and its individual components, to intervention with fluconazole. This is motivated by Blair et al. (2014) who reported that subjects who received antifungal treatment had a reduced time to full attendance at work and reduced time to 50% improvement in SF-36 Physical Component Score [13].

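### Secondary Objective 3 is worded as a between-arm comparison, but the plan gives no treatment difference or interval for the continuous FLEET CAP score or its components

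*Combined protocol and SAP*

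**What the plan says.** Section 3.1.2 states the objective as "To compare the clinical response and its individual components over time, by treatment group, in subjects with coccidioidomycosis pneumonia". Table 11 in Section 11.4.4.2 repeats it as "To compare the clinical response and its individual components by study group, over time, in subjects with coccidioidomycosis pneumonia".

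The outcome measure in that row is a set of within-arm statistics: "The mean, median, and quartiles of the FLEET CAP score at Days 22, 29 and 43 in each treatment group", and the same for each of the eight components. The main analytic strategy is "Descriptive and/or graphical summaries of the outcome measures by treatment group". On populations it says: "This analysis will be performed in both PP populations, both mITT populations, and the ITT population".

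Section 11.1 describes several of the secondary and exploratory objectives as "focused on validating the sensitivity of the composite score, and its individual components, to intervention with fluconazole". It adds that confirming or refuting the design assumptions may be the trial's main contribution.

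The table is presented as an outline: "Table 11 below briefly outlines the analytic approaches that will be taken for the secondary efficacy analyses", and "Details of the analyses will be described in the separate statistical analysis plan document".

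**The concern.** Sensitivity of a score to treatment is a between-arm difference judged against its uncertainty. The SO 3 row gives neither. It lists mean, median and quartiles by arm, with no between-arm contrast, no interval, no adjustment for the Day 1 score and no rule for missed visits. No standard deviation or standard error is listed, so a reader could subtract two means but could not form an interval from the listed outputs. Section 11.4.4.1 adds only tables and graphs for the composite score.

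If the responder comparison is inconclusive, the continuous score is the most informative efficacy data left, and the plan does not say how the arms will be compared on it. The components matter for designing a later trial, and no other analysis compares them between arms.

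Two further gaps sit in the same row. SO 3 is about cocci-positive subjects, but three of the five listed populations are not limited to them, and none is named as the one that answers the objective. Also, Section 11.2.1 assumes 20% drop-out before Day 22 among cocci-positive subjects. Observed-case means at Days 22, 29 and 43 could therefore describe different subsets of patients.

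**Working it through.** **1. What is compared between arms, row by row (Section 11.4.4.1 and Table 11)**

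| Item | Quantity | Between-arm method |
|---|---|---|
| Primary | Responder at Day 22 | Z test |
| SO 1 | Responder at Day 22, regardless of adherence | Primary analysis repeated |
| SO 2 | Responder at Day 43 | SO 1 analysis repeated, plus time-to-event |
| SO 6 | Responder at Day 22, all randomized | Non-inferiority by 95% CI |
| SO 3 | Composite score and eight components at Days 22, 29, 43 | Descriptive and/or graphical only |

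The table names inference where it is intended. The gap is the continuous composite and the components.

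**2. The plan's own power figure.** Inputs from Section 11.2.1: response 0.20 and 0.40, 100 per arm, two-sided 0.05, unpooled Z test.

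- SE = √(0.2×0.8/100 + 0.4×0.6/100) = √0.004 = 0.0632.
- Power = Φ(0.20/0.0632 − 1.960) = Φ(1.202) = 88.5%. The pooled form gives 87.6%, which is the Table 5 entry. The stated 88% reproduces.

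The plan states no power, SD or effect size for SO 3.

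**3. Precision available for a mean difference at one visit.** With 125 per arm in the cocci-positive mITT population and 20% drop-out, 125 × 0.8 = 100 per arm have a Day 22 score.

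- 95% CI half-width = 1.96 × SD × √(2/100) = 0.28 SD.
- Difference detectable with 80% power = (1.960 + 0.842) × SD × √(2/100) = 0.40 SD.
- The score runs from 0 to 22 (six items 0–3, two items 0–2). For assumed SDs of 3 to 6 points, the half-width is 0.8 to 1.7 points and the detectable difference 1.2 to 2.4 points.

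These figures are before baseline adjustment.

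**4. Power against the responder test.** One shortcut treats 20% versus 40% as a shift in a normal outcome: Φ⁻¹(0.40) − Φ⁻¹(0.20) = −0.253 + 0.842 = 0.588 SD. Then Φ(0.588 × √50 − 1.96) = Φ(2.20) = 98.6%. But response is a 50% reduction from baseline (Section 3.2.1), so this shift is in the proportion of the baseline score remaining. The Day 22 score is that proportion times the baseline score, and the spread of baseline scores adds noise.

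A simulation on the score itself makes the point. All of its inputs apart from the response rates and the 0–22 range are assumptions:

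- integer scores from 0 to 22, baseline mean 9, SD 3 to 4;
- proportion remaining normal with SD 0.2 to 0.4, with arm means set so that 20% and 40% fall at or below one half;
- scores rounded to whole points, which lifts both realised response rates slightly.

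| Analysis, 100 per arm, one visit | Power |
|---|---|
| Responder Z test | 87 to 90% |
| Mean score, unadjusted | about 68 to 92% |
| Mean score, adjusted for Day 1 score | about 97% |

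The gain depends on baseline adjustment. Without it, the mean comparison can do worse than the responder test.

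**5. Number of contrasts.** One composite plus eight components at three visits is 9 × 3 = 27. If all were tested at 0.05 and were independent, the chance of at least one false positive would be 1 − 0.95²⁷ = 75%. They are correlated, so this is an upper-end illustration.

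**The case against.** **The separate analysis plan may supply this.** Table 11 is an outline, the separate document was not available for this review, and baseline adjustment and missed-visit rules are the kind of detail it could hold. That stands for details. It does not change the strategy already named in the table: description for SO 3, inference for SO 1, SO 2 and SO 6.

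**Description is a coherent choice.** The SO 3 outcome measure is defined as within-arm statistics, the analysis matches it, and SO 4 and SO 5 are also descriptive. This is fair, and descriptive analysis of a secondary objective is acceptable. But SO 4 and SO 5 are worded as assessing, while SO 3 is worded as comparing, and Section 11.1 sets a validation aim for the score and its components.

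**A reader might infer that SO 3 cannot be answered at all.** The documents do not support that. The objective names clinical response, which is compared inferentially by the primary analysis, SO 1 and SO 2. Side-by-side means also give a point difference by subtraction. Nor do the design assumptions go unchecked: the planned responder analyses address the 0.20 and 0.40 rates directly.

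**A model brings its own issues.** The components are ordinal items scored 0–2 or 0–3, for which a linear model is a poor fit. A mixed model treats missed visits as missing at random, whereas Section 11.2.1 counts drop-outs before Day 22 as non-responders, so the two analyses estimate different things. Twenty-seven contrasts invite false positives. All three points stand, and the fix has to deal with them.

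**Conclusion.** The point holds for the continuous composite and the eight components. SO 3 is worded as a comparison, Section 11.1 asks whether the score responds to fluconazole, and the stated strategy yields neither an adjusted treatment difference nor an interval.

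The size is illustrative, because no FLEET CAP standard deviation is given. Under the assumptions shown, a baseline-adjusted comparison at one visit with 100 per arm has about 97% power, against about 88% for the responder test. A reader might infer a gain to 98.6% from the response rates alone. That figure applies to proportional change from baseline and does not carry over to a comparison of mean scores, which without adjustment has about 68 to 92%.

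The primary analysis, sample size and alpha are unaffected. This is an inexpensive improvement to a secondary analysis and does not threaten the trial's main conclusion.

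**What to change.** In Table 11, SO 3:

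- **Composite.** Make the main analysis a repeated-measures mixed model of the FLEET CAP score at Days 22, 29 and 43, with Day 1 score, treatment, visit and treatment-by-visit. Fit it in the cocci-positive mITT population, and report the adjusted treatment difference with 95% CI at each visit.
- **Components.** Report between-arm differences with 95% CI, by an ordinal method or a simple mean difference. Label them supportive, with no multiplicity control and no significance claims.
- **Missing scores.** State that the model treats missed visits as missing at random, and that this differs from the non-responder rule for the responder analysis in Section 11.2.1.
- **Other populations.** Keep the descriptive tables.

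The cost is one standard model and a set of unadjusted supportive intervals. The scores are already scheduled on Days 1, 22, 29 and 43.

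Rewording the objective so that it only describes would remove the mismatch at no cost, but would leave the aim in Section 11.1 without an estimate.
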